
Patients diagnosed by the LRTC with PTSD, receiving evidenced based combined pharmacological and psychotherapy (either PE or CPT)
	
 1) Male or female English-speaking active duty or recently retired veteran patients who have deployed post 9/11 receiving treatment at LRTC between the ages of 18-65 years; 2) Patients must have a diagnosis of PTSD confirmed by the Clinician-Administered PTSD Scale (CAPS-5) at screening, 3) Subjects must have a minimum PTSD Symptom Checklist for DSM-V (PCL-5) symptom severity rating of 25. 	
 1) Subjects with a diagnostic history of bipolar disorder, schizophrenia or schizoaffective disorder as documented in the medical record. 2) Substance use disorder during the 12 months prior to screening; except that Mild - Moderate, but not Severe, Alcohol Use Disorder (using DSM-5 criteria) will be allowed as determined by LRTC medical provider review. 3) Any history or signs of serious medical or neurological illness including seizure disorders. Except for seizures, a subject with a clinical abnormality may be included only if the study clinician considers the illness will not introduce additional risk and will not interfere with the study procedures. This will be determined during the screening phase via self-report and/or medical history review. 4) History of traumatic brain injury (TBI) with loss of consciousness for 20 minutes or more as determined by the History of Head Injuries questionnaire. 5) Females will be excluded if they are pregnant (i.e. positive pregnancy test identified after their LRTC intake). 6) Any history or signs of metal objects deemed unsafe for MRI or that may adversely affect image quality of the brain region (e.g. surgical clips, cardiac pacemakers, metal implants, etc.) in the body at the time of screening as indicated by self-report. MRI can have risks for persons with foreign bodies implanted in their body.

Item 6
Research Plan / Description of the Research Methods a. *Provide a comprehensive narrative describing the research methods.*
Provide the plan for data analysis (include as applicable the sample size calculation).

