Post-treatment MRI. Immediately following the last irTMS treatment at the end of the 3rd week, a second functional MRI scan will be conducted to assess treatment effects. The post-MRI will occur any time after last treatment with up to a 3-day window for completion. In rare instances, if scheduling circumstances (such as weekends and institution holidays, MRI staff outages, participant discharge date) prevent the post-MRI from occurring after all treatment sessions have been completed, the post-MRI may be conducted before the final treatment session, and any remaining treatment sessions will occur after the post-MRI. This will be documented in the participant study file and will be considered during data analysis. After the post-treatment MRI session, each patient will also undergo another brief motor threshold assessment in order to document any changes which may be used to report on the safety of this TMS treatment protocol. This second scanning visit should take approximately 1 hour.

Participant Blind Form. The Participant Blind Form measures the participant's best guess about the study treatment that they received, level of confidence in this guess, and how unblinding could potentially have occurred. This form will be used at treatment completion and follow-up for all CAP RCTs that are double-blind (i.e., medication studies).

Independent Evaluator Blind Form. The Independent Evaluator Blind Form measures the independent evaluator's best guess about the study treatment that the subject received, level of confidence in this guess, and how unblinding could potentially have occurred.

Phase III: 1 Month/3 Month Follow-Up

One month and three months after the final iTMS treatment session, participants will be interviewed (either in-person or over the telephone) by a member of the research team. Self-report measures may be administered over the phone or by direct electronic data capture via a secure link to the secure STRONG STAR database.

Table of Study Procedures:

Phase	Pre-Study (at LRTC)			3 Week Treatment (at LRTC & the RII)			Post-Treatment (at the RII)	1 Month/3 Month Follow-Up (either in-person or via telephone)
	Wk 0			Wk 1	Wk 2	Wk 3	Wk 3	Wk 7/Wk15
	LRTC Intake	Baseline	MRI Appt					
	Day(s)	0 to 1	1-3	2-3	7	14	20	21 -24
Medical History	X							
Metal Screening		X						
Informed Consent		X						
1. Demographics & Military Service Characteristics		X						
2. History of Head Injuries Screening		X						

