- Rare and Serious. In 100 people, approximately 1-2 may have:
 - Seizures

Risks and Side Effects related to the Robot placement of the iTMS include those which are:

- Rare and Serious. In 100 people, approximately 0-1 may have:
 - Physical injury from the robotic device.

Risks and Side Effects related to the MRI include those which are:

- Rare and Not Serious. In 100 people, approximately 1 may have:
 - Claustrophobia (fear of tight spaces). During the MRI scan, participants will be asked to remain perfectly still.
- Rare and Serious. In 100 people, approximately 1-2 may have:
 - Foreign bodies which may interact with the magnetic field of the MRI

Risks related to the Psychological Assessments include those which are:

- Less likely (less than 5-20 subjects out of 100) and Not Serious:
 - Emotional distress including experiencing an initial increase of PTSD symptoms due to the discussion of traumatic events.
- Rare (less than 5 subject out of 100) and Serious:
 - Breach of confidentiality.

Risks of having a diagnosis of PTSD regardless of participation in this research or not: Individuals with PTSD may have suicidal thoughts or attempt suicide. This is a risk to you whether you are being treated for PTSD or not. Therefore, the risk of suicide is not any higher in the study than it would be if you were not in this study.

Risk Minimization.

- To physical injury by the robotic device. Robotic devices must be used with caution in the presence of persons. The robotic device used here (KUKA®) poses no significant risk. The KUKA® moves slowly, so that it can easily be stopped prior to any collision. Loss of electrical power renders the KUKA® robot immobile in its current position, (i.e., it does not return to a “parking” position or make any sudden motions). The KUKA® robot requires a key and a recessed button to actuate, being used only under direct supervision. Collectively, these features make the KUKA® robot safe for use by and with humans.
- To claustrophobia in the MRI.
- To injury during the MRI from foreign bodies interacting with the magnetic field. MRI can have risk for persons with foreign bodies implanted in their body. Cardiac pacemakers and cochlear implants may cease to function and can be permanently damaged by the MRI. Surgical clips on aneurysms and intestines may be moved by the magnetic field. Ferrous metal filings in the eye (e.g., in machinists) can be

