moved by the magnetic field. Foreign body risk is minimized by including only volunteers with no known foreign bodies and no exposure to circumstances, which might predispose to foreign bodies (e.g., metal machine workers). Before receiving an MRI, participants will be asked about any metal objects that may be in their body.

- To emotional distress during psychological assessments. All clinical staff associated with assessment have experience in psychiatric evaluation and will implement protocol procedures in a sensitive and supportive manner. Interviews will be stopped if subjects become distressed or object to answering questions. Measures implemented to minimize risks are: 1) Before participating, subjects undergo careful psychiatric and medical evaluation. 2) An experienced study clinicians are available at all times during the sessions to provide medical a psychiatric monitoring for subjects experiencing any difficulties during treatment. 3) All subjects will be seen weekly for ongoing assessment of behavioral symptoms. 4) If a subject's clinical condition significantly worsens, he or she will be withdrawn from the research protocol to continue TAU at LRTC. Any indication that a participant's suicidality has worsened from baseline will be handled using processes at the LRTC.
- To breach of confidentiality. Study participants will be treated in individual offices located on the LRTC. Data a will be stored by an assigned participant code number so that data records and specimens can be viewed by password-authenticated, authorized investigators and Consortium personnel. Digital audio recordings of assessments will be labeled with the participant's study id number and saved on a secure password protected server. Those recordings to be reviewed for fidelity to ensure that the assessment is being delivered in accordance with Consortium standardized procedures. There is no option for the reviewers to download or otherwise save the recordings to their computers. Every member of the Research Team will be trained and monitored about how to handle and protect both medical and research records. Only authorized study staff, and members of the Data Management and Biostatistics Core will have access to either the raw data or electronic study data.

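### The risk text says nobody with a known foreign body or a predisposing exposure is included, but exclusion criterion 6 is narrower and has no exposure condition

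*Combined protocol and SAP*

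**What the plan says.** Two places in the combined protocol and SAP state who may enter an MRI scanner in this trial.

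Item 5, exclusion criterion 6, removes a person with "Any history or signs of metal objects deemed unsafe for MRI or that may adversely affect image quality of the brain region". The object must be "in the body at the time of screening as indicated by self-report". The examples given are surgical clips, pacemakers and metal implants. Exposure to metal is not mentioned in this criterion or in any other entry in the eligibility lists.

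Item 6, Risk Minimization, under injury from foreign bodies during the MRI, says that the risk is reduced by "including only volunteers with no known foreign bodies and no exposure to circumstances, which might predispose to foreign bodies". The example of such exposure is metal machine workers. The same entry adds that before an MRI "participants will be asked about any metal objects that may be in their body".

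Two other places bear on the point. The Table of Study Procedures has a "Metal Screening" row, marked once, at Baseline, with no description of what is asked. The list of MRI risks has the entry "Foreign bodies which may interact with the magnetic field of the MRI", under a rare and serious heading at about 1 to 2 in 100 people.

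**The concern.** The risk text is worded as a statement about who is included, so it works as an eligibility rule. It is not the rule in the eligibility list. The protocol offers the exposure condition as a protection, and its own reason is visible nearby: it names iron filings in the eyes of machinists as something the magnet can move. A person may carry such a fragment without knowing it, and a question about known objects cannot find it.

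If staff work from the eligibility list, the protection described in the risk section is not applied by any written step. If they work from the risk section, they turn away people whom the list does not exclude. Either way the protocol does not give one answer, on a hazard that it lists as serious, in a trial that schedules an MRI session before treatment and another after it.

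**Working it through.** The plan gives no figure to reproduce, and no calculation applies. The check is to set the two rules side by side, put the same people through both, and look for text that reconciles them.

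**The two rules**

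| Feature | Item 5, exclusion 6 | Item 6, Risk Minimization |
|---|---|---|
| Known foreign body | Excluded only if metal and either unsafe for MRI or liable to affect brain images | None allowed |
| Predisposing exposure, no known object | Not addressed | Not allowed |
| Source of information | Self-report | Participant is asked about metal objects in the body |

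**Four people put through both**

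| Person | Exclusion 6 | Risk text | Agree? |
|---|---|---|---|
| Reports a metal object unsafe for MRI | Excluded | Not includable | Yes |
| No known object, no predisposing exposure | Not excluded | Includable | Yes |
| Metal machine worker, no known object | Not excluded | Not includable | No |
| Known foreign body judged MRI-safe and harmless to image quality | Not excluded | Not includable | No |

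The third person is the protocol's own example, so that conflict needs no inference. The fourth follows from the qualifiers in exclusion 6, which the risk text lacks.

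**Is there a bridge between the two?**

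1. The opening of exclusion 6, which refers to history or signs, sounds broad. Grammatically it governs metal objects in the body at screening, so exposure alone is not reached.
2. The pre-MRI question in the risk text covers objects, not exposure. It does not carry out the condition stated in the sentence before it.
3. The Metal Screening row might ask about exposure, but the documents do not say so. If it did, and staff acted on the answer, it would remove people whom exclusion 6 does not.
4. The Pre-Screening section has staff review the basic inclusion and exclusion criteria, and Step-by-Step Methods has eligible subjects who meet the inclusion criteria randomized. Both point to the Item 5 list rather than to the risk section.

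No bridge is stated.

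**Can the size be worked out?** No. It would need the share of screened patients with a predisposing exposure and no known object, plus the share with a known but acceptable foreign body. The documents give neither. The 1 to 2 in 100 in the risk list describes foreign bodies that may interact with the magnet. People who report an unsafe metal object are barred by both rules, so that rate does not measure the disagreement. The protocol also does not say whether it applies before or after screening.

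**The case against.** The best reply is that the passages can be obeyed together. Exclusion 6 lists reasons to exclude and does not require anyone else to be admitted. The risk text, in the same approved protocol, adds a condition, and staff who apply the stricter wording satisfy both. There are also other checks: the Metal Screening step before the MRI appointment, the medical history taken at intake, and a general statement, in the entry on emotional distress, that subjects are medically evaluated before taking part. On this view a condition was simply not carried into a list.

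Part of this stands. Applying the stricter text is possible, and it cannot be said that the Metal Screening step is deficient, because its content is unknown. But the screening and randomization text points to the listed criteria, and none of the other checks is said to ask about exposure. A protection that depends on staff noticing a sentence in the risk section has no stated route into practice.

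Some stronger readings are tempting, and the documents do not support them:

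- Because participants are "active duty or recently retired veteran patients who have deployed post 9/11", a reader might infer that many have blast or fragment exposure and fall between the two rules. The documents name no such exposure; the only example is metal work. If deployment exposure counted, the risk text could bar much of the population the trial recruits, so that reading is doubtful.
- A reader might multiply the 1 to 2 in 100 by the number screened or randomized. As shown in the working, that rate measures something else.
- A reader might expect practice to vary between sites. Recruitment is at one treatment center and imaging at one institute.
- A reader might conclude that self-report is an inadequate source for exclusion 6. The two passages do not conflict on this, since both rely on what the participant says.

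**Conclusion.** The inconsistency is real and on the face of the text. Exclusion 6 is narrower than the safeguard in the risk section in two respects: it has no exposure condition, and it tolerates a known foreign body judged MRI-safe and harmless to image quality. At least two kinds of person are therefore treated differently, and no written screening step carries the exposure condition.

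The number of people affected is unknown and is left unstated here. The point matters because the protocol itself lists the hazard as rare and serious, and because it presents the exposure condition as the protection. It has no bearing on the sample size or the analysis. Eligibility and the baseline MRI are described ahead of random assignment, so the comparison between arms is not touched.

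The conclusion rests on two readings: that a sentence saying who is included is meant as a rule, and that exclusion 6 does not reach exposure alone. It does not show that screening in practice omits exposure, only that the documents do not provide for it.

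**What to change.** Reconcile exclusion criterion 6 in Item 5, the Metal Screening step in the Table of Study Procedures, and the foreign-body entry under Risk Minimization, so that all three state one identical criterion. It should settle both open questions: whether predisposing exposure without a known object excludes a person, and whether any known foreign body does or only one that is unsafe or affects the images. The Metal Screening step should then say what it asks, so that the criterion can be applied from the form. Which criterion stands is for the sponsor and the MRI safety lead to decide.

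The cost is a minor amendment. If the exposure condition is kept, one or two questions may be needed on the existing metal screen, and there may be a few more screen failures. No change to the sample size or the analysis plan is needed.

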Step-by-Step Methods: We propose to test 100 patients (i.e. 50 per arm) who meet criteria for PTSD as determined by the Clinician Administered PTSD Scale (CAPS-5) and the outlined study inclusion criteria. We anticipate consenting and screening approximately 200 male and female subjects, in order to meet the target enrollment goals. To account for subject dropouts and retain a sample of 100 subjects completing the double-blind treatment phase (50 per treatment group), 132 eligible subjects (66 in each group) meeting the study inclusion criteria will be randomized for the study. See also Table of Study Procedures below.

Recruitment

Patients will be recruited at LRTC from institution's PTSD inpatient program by the study staff supervised by the On-site Investigator's team. Upon admission to the LRTC, patients will be informed about this treatment trial by either their staff psychiatrist or a member of the LRTC's research team. Each patient will be given an information sheet describing the study. If interested in participating, each patient will be shown a video describing the treatment trial and each of the tools/treatments used throughout the study (i.e. MRI and TMS).

Pre-Screening and LRTC Intake

Under an IRB approved HIPAA Waiver of Authorization, Waiver of Informed Consent, and Waiver of Documentation of Informed Consent, study personnel will conduct a brief pre-screening intake interview where the basic study inclusion and exclusion criteria will be reviewed to help the individual determine if he or she meets the study criteria or has obvious exclusions from the study protocol. This information will be maintained as a secure file with the following information: name, phone number, name of study, referral date, referral source, potential eligibility status, reason if not eligible, and verbal permission to contact the caller in the future for other studies. Subjects who agree to study participation will sign a consent document before any further screening will take place. Any individually identifiable information and Protected Health Information (PHI) collected on individuals who do not consent to participation will not become part of the research data. If subjects agree to participate in the research, the identifiable data collected will become part of the subjects' research records and will be stored according to the research confidentiality plan.

Consent Process

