Clinical Outcomes Data Analysis plan. All pre-treatment and post-treatment MRIs will be acquired and analyzed at the RII, however, all of the statistical analysis of the symptom scores for this project will be done upon completion of recruitment and termination group blinding. The primary efficacy outcome measure will be the PTSD Checklist (PCL-5) for symptoms assessed pre-treatment, weekly during treatment, post-treatment, and 1-month following the completion of treatment and the Clinician-Administered PTSD Scale for DSM-5 (CAPS-5) for the diagnosis of PTSD assessed pre-treatment and 1-month following the completion of treatment. The primary analysis will use mixed effects regression models. Secondary analysis will focus on changes in PTSD symptoms clusters, effects of the intervention in mood symptoms, functioning and cognitive outcomes. Types and rates of adverse events will be summarized and compared across the study groups. The durability of benefit and the clinical significance of PCL changes will be explored. Non-compliance to protocol as defined as missing two consecutive iTMS sessions or receiving less than 16 iTMS sessions during hospitalization at LRTC will be assessed for and evaluated in data analysis.

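### The dropout allowance behind 132 randomised runs only to the end of treatment (about Week 3), while the analysis plan and schedule first re-measure the primary CAPS-5 at 1 month (Week 7), with no allowance for loss in between

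*Combined protocol and SAP*

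**What the plan says.** Item 6, Step-by-Step Methods, gives the test size: "We propose to test 100 patients (i.e. 50 per arm) who meet criteria for PTSD". It then inflates the number to be randomised for dropout: "retain a sample of 100 subjects completing the double-blind treatment phase (50 per treatment group), 132 eligible subjects (66 in each group". No dropout rate, alpha, power, effect size or standard deviation is given.

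Item 6, Clinical Outcomes Data Analysis plan, names two primary efficacy measures. The PCL-5 is taken before treatment, weekly, after treatment and at 1 month. The CAPS-5 is "for the diagnosis of PTSD assessed pre-treatment and 1-month following the completion of treatment". The Table of Study Procedures agrees: the CAPS-5 is marked at baseline and in the 1 Month/3 Month column (Wk 7/Wk 15), and nowhere between.

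The CAPS-5 description under Phase I: Baseline Assessment says something different. There, blinded independent evaluators give it at the start and at the end of the intervention.

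Phase III describes how follow-up is done: "One month and three months after the final iTMS treatment session, participants will be interviewed (either in-person or over the telephone".

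On early stopping, the irTMS Treatment Protocol text says participants who cannot tolerate treatment are withdrawn from the study. Discontinuation of Subjects allows discontinuation from both treatment and assessments. The analysis plan says that non-compliance, including fewer than 16 sessions, will be evaluated in the analysis. It gives no rule for following those participants to 1 month.

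**The concern.** A dropout allowance should run to the time point at which the outcome is measured. Here it stops about four weeks short of the first post-baseline CAPS-5 in the analysis plan and schedule. Participants are inpatients during treatment; afterwards they are reached in person or by telephone, so some loss after Week 3 is plausible.

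The CAPS-5 is the primary measure rated by blinded evaluators. With one post-baseline value in the primary plan, a mixed model has no intermediate CAPS-5 visit to draw on when the 1-month value is missing. A retention target counted at treatment completion could therefore be declared met while the 1-month CAPS-5 comparison has fewer than 50 per arm, and the plan would not show it.

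**Working it through.** **Inputs from the documents.** Target 100 (50 per arm); randomised 132 (66 per arm); allowance defined to the end of the treatment phase, about Week 3; first post-baseline CAPS-5 at Week 7 in the analysis plan and schedule.

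**Assumption.** L, the fraction of treatment completers without a 1-month CAPS-5. The documents give no value; I use 0% to 20%.

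**Step 1: reproduce 132.** No rate is stated, so it can only be solved for: 1 − 100/132 = 32/132 = 24.2%. Inflating by n/(1 − d) with d = 24%: 50/0.76 = 65.8, rounded up to 66 per arm, or 132. With d = 25% it is 67 per arm, or 134; with d = 20%, 63 per arm, or 126. The figure fits a loss of about 24% during treatment.

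**Step 2: CAPS-5 number at 1 month if all 32 are lost in treatment and none is assessed later.** N = 100 × (1 − L); total attrition = 1 − N/132.

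| L | N with 1-month CAPS-5 | Per arm | Total attrition |
|---|---|---|---|
| 0% | 100 | 50 | 24.2% |
| 5% | 95 | 47.5 | 28.0% |
| 10% | 90 | 45 | 31.8% |
| 15% | 85 | 42.5 | 35.6% |
| 20% | 80 | 40 | 39.4% |

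Only L = 0 delivers 50 per arm under this condition.

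**Step 3: what following non-completers would recover.** If a fraction f of the 32 is assessed at 1 month, N = 100 × (1 − L) + 32f. N returns to 100 when 32f = 100L: 10 of the 32 at L = 10%, 20 of the 32 at L = 20%. Put another way, if all 132 are sought, up to 32 (24.2%) can be missing at 1 month for any reason and 100 remain.

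**Step 4: power, for illustration only.** Assume two-sided alpha 0.05, a continuous score, and the effect that 50 per arm would detect with 80% power: d = (1.960 + 0.842) × √(2/50) = 0.560. Power at n per arm is Φ(d√(n/2) − 1.960). At 45 per arm: 0.560 × √22.5 = 2.658, giving 75.7%. At 40 per arm: 0.560 × √20 = 2.506, giving 70.7%. None of these settings is in the documents. The plan specifies mixed effects regression and links the CAPS-5 to diagnosis, so the planned analysis may not be of a continuous score.

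**The case against.** Four arguments count against the point.

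- **The CAPS-5 may be given at the end of treatment.** The instrument description says so, and if it governs, the gap closes. But that description also covers other sites and remote studies, so it reads as consortium-wide text. The trial's own analysis plan and schedule both say 1 month, and the schedule puts the Independent Evaluator Blind Form in the follow-up column. The 1-month reading is the better supported, but the conflict stands and has to be resolved first.
- **No promise is broken.** The plan offers 100 treatment completers; it does not say that 100 will have a 1-month CAPS-5. That is correct, and for the PCL-5, measured weekly and after treatment, a completer count is a reasonable match. The point is confined to the CAPS-5 for that reason.
- **Non-completers may still be assessed.** Discontinuation from assessments is permitted, not required in every case. Treatment is for up to 20 sessions while hospitalised, so early discharge is not in itself withdrawal. The analysis plan expects some data from people with few sessions. This stands: the documents leave open whether the 32 contribute at 1 month.
- **No rate or power is stated.** Also correct. All 32 losses need not occur, and there is no stated power to fall short of.

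A reader might infer that the CAPS-5 comparison will have fewer than 50 per arm, or that the trial is underpowered. The documents support neither. The first needs the full 24.2% loss, no 1-month data from those participants, and further loss. The second has no stated benchmark. Nor is there support for projecting the treatment-phase loss forward at the same weekly rate: intolerance of irTMS and the burden of daily sessions end with treatment, and follow-up can be by telephone.

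**Conclusion.** The point holds in a limited form. The retained sample of 100 is counted at a time point that does not match the first post-baseline CAPS-5 in the analysis plan and schedule, and no allowance covers Week 3 to Week 7. If treatment-phase loss reaches the implied 24.2% and those participants are not assessed afterwards, 50 per arm at 1 month requires no further loss; an assumed 5% to 20% leaves 95 to 80. If treatment-phase loss is lower, or enough non-completers are assessed, the 100 can still be reached.

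The conclusion rests on the 1-month CAPS-5 timing governing over the instrument description. The numerical range rests on an assumed later loss. This is a gap in definition and follow-up rules that should be closed, not a demonstrated shortfall.

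**What to change.** 1. **Reconcile the CAPS-5 timing** across the instrument description, the Table of Study Procedures and the Clinical Outcomes Data Analysis plan.
2. **Separate stopping irTMS from stopping assessment.** Keep 132 randomised. State in Step-by-Step Methods, the irTMS Treatment Protocol, Discontinuation of Subjects and the analysis plan that every randomised participant who has not withdrawn consent is sought for the 1-month CAPS-5 and PCL-5, by telephone where needed. Define the visit date for those who stop early. This concerns data collection only and leaves the criteria for stopping treatment as they are.
3. **Define and track the retained 100 as participants with a completed 1-month CAPS-5**, and state the assumed total loss and its time point. If the sponsor decides not to follow non-completers, restate the expected CAPS-5 number as 100 × (1 − assumed Week 3-to-7 loss), for example 90 at 10%. Label any accompanying power figure as illustrative unless its inputs are given.

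The cost is wording in several sections and some extra follow-up contacts with people who stopped irTMS. No one is added to the randomised number. If non-completers are not followed, the stated CAPS-5 number becomes smaller and less favourable.
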